All endpoints will be descriptively summarized and their correlation with biomarkers and efficacy endpoints explored via regression models as appropriate. One interim efficacy analysis is planned 13 weeks after the 40th subject is enrolled. Final analysis will be conducted 12 months after last subject is enrolled.

Sample Size Justification:

Prior clinical trials data in the post-chemo setting have shown the following median rPFS for subject randomized to initial placebo, placebo+prednisone, or mitoxantrone+prednisone therapy:

- AFFIRM: Placebo = 2.9 months
- COU-301: Placebo + Prednisone = 3.6 months
- TROPIC: Mitoxantrone + Prednisone = 1.4 months

With a sample size of 40 subjects and an assumed median rPFS of 4 months for the therapy defined in this single-arm study, approximately 34 events are expected over a 12-month accrual and 12-month minimum follow-up. Further assuming uniform accrual, 10% loss to follow-up, and an exponential distribution for the rPFS event times the expected lower bound of the 90% confidence interval for the median is approximately 2.5 months based upon simulations.

Safety:

The severity of all adverse events will be evaluated by the investigator based on the National Cancer Institute's Common Terminology Criteria for Adverse Events (NCI-CTCAE), version 4.0 and all adverse events will be coded to preferred term, higher level term, and system organ class using the Medical Dictionary for Regulatory Activities (MedDRA). The number and percentage of subjects with adverse events will be presented by MedDRA system organ class and preferred term, relationship to study treatment, and maximum CTCAE grade. Descriptive statistics will be used rather than inferential statistics.

Laboratory values will be classified by toxicity grade based on the NCI¬CTCAE, version 4.0. Tables of laboratory CTCAE grade shift from baseline to maximum CTCAE grade across subsequent visits will be provided.

Correlative Studies:

Objectives:

- Explore the prevalence and dynamics of resistance biomarkers
- Explore potential correlation of the resistance biomarkers with rPFS, PSA response, and PSA progression

- Explore potential correlation of the sensitivity biomarkers with rPFS, PSA response, and PSA progression
- Explore potential correlation of inflammatory proteins with rPFS, PSA response, and PSA progression
- Explore potential correlation of AR and glucocorticoid receptor levels and mutations/polymorphism with rPFS, PSA response, and PSA progression

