- j The window for all radiological assessments is ± 7 days. At Weeks 9, 17, 25 and subsequent assessments prior to treatment discontinuation, all other procedures must be completed within the ± 3 day window. Bone progression at the first reassessment at Week 9 requires a confirmatory scan 6 or more weeks later.
- k Adverse events, serious or non-serious, will be collected from the time the patient signs the consent form until the Safety Follow-Up visit, regardless of initiation of another anti-neoplastic therapy prior to last dose of enzalutamide.
- l Long-term follow-up for radiographic progressions (until progression or initiation of new anti-neoplastic therapy), survival, and subsequent anticancer therapies should be performed every 12 weeks for a maximum of 3 years from first dose. The study will end when the last subject has been followed for 1 year from date of first dose.
- m Enzalutamide will be administered until the disease progression, including radiographic progression or unequivocal clinical progression. Per the Investigator's clinical judgment and with sponsor approval, patients may be allowed to continue enzalutamide until the next treatment is initiated. If another non-cytotoxic, non-investigational, antineoplastic agent is initiated after protocol-defined progression has been determined, enzalutamide may be continued per the Investigator's clinical judgment and with sponsor approval as long as the patient is tolerating enzalutamide and continues androgen deprivation therapy
- n Blood samples for CTC molecular profiling and serum samples will be collected at baseline, week 13, time of PSA progression, and time of radiographic progression.

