5.4 Biomarker Analysis Set (BAS)

The Biomarker analysis set (BAS) consists of the subset of the FAS population for which biomarker data are available to facilitate derivation of at least one of the correlative biomarkers. The Total N used in summaries and analyses for each unique biomarker will be the number of subjects with data available for that unique biomarker.

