6.1.3 Exploratory Efficacy Endpoints

Samples were collected serially at baseline, week 13, at time of PSA progression, and time of radiographic progression and analyzed at central labs for:

- 1) Androgen receptor
 - a. AR-V7
 - b. AR-FL
 - c. AR-V7/AR-FL ratio
- 2) Glucocorticoid receptor
 - a. GR-FL
- 3) AR mutations;
 - a. L702H
 - b. W741C
 - c. F876L
 - d. T877A
- 4) Circulating tumor cell detected
- 5) Inflammatory biomarkers
 - a. IL6
 - b. IL8
 - c. TNF- α (tumor necrotic factor alpha)
 - d. sTNFR1 (soluble TNF receptor-1)
- 6) Neuroendocrine biomarkers
 - a. CgA (chromogranin A)
 - b. NSE (neuron specific enolase)
 - c. Synaptophysin

Other biomarkers may be identified for analysis and SAP will be amended accordingly prior to database lock.

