7.4.3 Analysis of Exploratory Endpoints

Unless otherwise noted, all continuous biomarker values will be summarized after log base 2 transformation. Descriptive statistics (e.g., N, mean, standard deviation, minimum, median, maximum for continuous variables; or N, frequency, and percentage for categorical variables) will be provided for baseline blood and plasma samples and by each post-baseline scheduled time point for the following endpoints;

1. AR-V7 (positive/negative status, continuous log base 2 for positive status only)
2. AR-V7 status change from baseline during the study (unchanged, positive to negative, negative to positive)
3. AR-V12/v567es (positive/negative status, continuous log base 2 for positive status only)
4. AR-V7 positive or AR-V12 positive (yes/no)
5. AR-FL (continuous log base 2)
6. Ratio of (log base 2 AR-V7)/(log base 2 AR-FL) (for positive status AR-V7)

7. GR-FL (continuous log base 2)
8. L702H (yes/no, only descriptive statistics)
9. W741C (yes/no, only descriptive statistics)
10. F876L (yes/no, only descriptive statistics)
11. T877A (yes/no, only descriptive statistics)
12. CTC detected (yes/no)
13. IL6 (continuous log base 2)
14. IL8 (continuous log base 2)
15. TNF- α (tumor necrotic factor alpha) (continuous log base 2)
16. sTNF R1 (soluble TNF receptor-1) (continuous log base 2)
17. CgA (chromogranin A) (categorical split TBD, continuous log base 2)
18. NSE (neuron specific enolase) (categorical split TBD, continuous log base 2)
19. Synaptophysin (categorical split TBD, continuous log base 2)

Three baseline binary AR predictors: 1) AR-V7 status; 2) a composite status (yes/no) of either AR-V7 positive or AR/V-12 positive; and 3) CTC status will be assessed individually, as independent variables, to predict rPFS, time to PSA progression, OS, and composite progression free survival (cPFS) using a single variable Cox model.

Multivariable AR Cox models will then be run on the same endpoints:

- 1) Using log base 2 transformed baseline AR-FL as a covariate in combination with baseline AR-V7 status;
- 2) Using log base 2 transformed baseline AR-FL as a covariate in combination with baseline composite AR-V7/V12 response;

Four baseline continuous log base 2 transformed inflammatory cytokine predictors: 1) IL6, 2) IL8, 3) TNF- α , and 4) sTNF R1 will be assessed individually, as independent variables, to predict rPFS, time to PSA progression, OS, and composite progression free survival (cPFS) using a single variable Cox model.

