7.5.2 Clinical Laboratory Evaluation

Quantitative clinical laboratory variables, i.e., hematology, biochemistry, and urinalysis will be summarized using mean, standard deviation, minimum, maximum and median at each visit. Additionally, a within-subject change will be calculated as the post-baseline measurement minus the baseline measurement and summarized in the same way. Baseline is defined as the last available measurement prior to the first study drug dose.

Frequency tabulations of qualitative clinical laboratory variables (urinalysis) will be presented at each visit.

Laboratory results will also be graded using NCI-CTCAE, where possible. Parameters that have criteria available for both low and high values, i.e., hypo- and hyper-, will be summarized for both criteria. The same subject can be counted for both values if the subject has different laboratory values meeting each criterion. NCI-CTCAE grade of laboratory evaluations will be summarized by number and percentage of subjects for each visit. Shift

tables of lab parameters NCI-CTCAE grade change from baseline to worst post-baseline grade will also be presented.

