7.11.1 Missing Data

As a general principle, no imputation of missing data for other variables will be done. Exceptions are the start and stop dates of AEs and concomitant medication. If day is missing from any date in a derivation then calculate the derived value using 15th day of month. If month or year is missing from any date in a derivation then set the derived value to missing.

Adverse events with missing relationship will be summarized as 'Related to Study Drug'. Adverse events with missing severity grade will be handled as 'missing'.

Incomplete onset dates default AEs to treatment emergent. Listings of the AEs and concomitant medications will present the actual partial dates; imputed dates will not be shown.

Cases where the onset date of an AE is (partially) missing, will be addressed prior to or during the DRM in order to determine whether the AE must be considered treatment emergent or not.

Imputation on missing date of initial diagnosis (cancer duration) and cancer treatment history (start date, stop date, or date of procedure) will be done as follows:

- Incomplete Day: use the 15th day of the month
- Incomplete Month: use 1st of July if the Year is before Year of dosing, otherwise missing.
- Incomplete Year: no imputation, the derived variable is considered to be missing.

Imputation methods will not be used to determine other endpoints.

Listings will always show the original date information without imputation, but derived parameters (TEAE indicator, start day, end day, study day) will be flagged.

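### Outside AR-V7 status, SAP 7.4.3 plans no within-patient change for any biomarker and does not say how the progression samples are summarised

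*SAP*

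**What the plan says.** The correlative objectives in the protocol synopsis include "Explore the prevalence and dynamics of resistance biomarkers". SAP 6.1.3 describes the sampling: "Samples were collected serially at baseline, week 13, at time of PSA progression, and time of radiographic progression".

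SAP 7.4.3 then plans descriptive statistics that "will be provided for baseline blood and plasma samples and by each post-baseline scheduled time point for the following endpoints". Nineteen items follow. Item 2 is a within-patient measure: "AR-V7 status change from baseline during the study (unchanged, positive to negative, negative to positive". No change from baseline is listed for AR-V12, the AR-V7/AR-V12 composite, AR-FL, the AR-V7/AR-FL ratio, GR-FL, the four AR mutations, CTC detection, the four inflammatory markers or the three neuroendocrine markers.

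Under SAP 5.4 the N for each marker "will be the number of subjects with data available for that unique biomarker". SAP 7.11.1 states: "As a general principle, no imputation of missing data for other variables will be done". For laboratory tests, by contrast, SAP 7.5.2 says that "a within-subject change will be calculated as the post-baseline measurement minus the baseline measurement", and SAP 7.5.3 does the same for vital signs.

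In both schedule tables, Week 13 is the only marked post-baseline biomarker visit. The two progression samples appear only in a footnote. Protocol 7.9 refers to the SAP for visit windows, and SAP 7.11.3 says these are not applicable.

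**The concern.** Dynamics means change within patients. A table with one column for baseline and one for Week 13, each over whoever has a sample, mixes two things: change in patients who were sampled twice, and a change in who is being sampled.

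The second part matters if subjects without a Week 13 sample differ at baseline. SAP section 2 states the default for stopping: "Enzalutamide will be administered until the disease progression, including radiographic progression or unequivocal clinical progression". A subject who stops before Week 13 moves to safety and long-term follow-up, where the schedule marks no biomarker sample other than those tied to progression. If high marker values go with early progression, those remaining at Week 13 have lower values than the whole cohort had at baseline. A reader could then take the fall as re-treatment suppressing a resistance marker.

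The progression samples carry the information on acquired resistance. A summary by *scheduled* time point gives them no clear place.

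**Working it through.** **1. The plan's own figure.** Inputs from SAP section 4: N = 40, exponential rPFS with a 4-month median, uniform 12-month accrual, 12-month minimum follow-up, 10% loss.

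- λ = ln 2 / 4 = 0.1733 per month.
- Mean event-free probability over follow-up of 12–24 months = (e^(−12λ) − e^(−24λ)) / (12λ) = (0.1250 − 0.0156) / 2.079 = 0.0526.
- Expected events = 40 × 0.90 × (1 − 0.0526) = 34.1. The plan says about 34, so the inputs are read as intended.

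**2. Events before Week 13.** Day 57 (the Week 9 scan) is 56/30.4375 = 1.840 months after Day 1. Day 85 (Week 13) is 84/30.4375 = 2.760 months.

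- By Week 9: 1 − e^(−0.1733 × 1.840) = 27.3%, or 10.9 of 40.
- By Week 13: 1 − e^(−0.1733 × 2.760) = 38.0%, or 15.2 of 40.

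So up to about 11–15 subjects could lack a Week 13 sample, leaving about 25–29. With the two AFFIRM medians given in Protocol 1.2, the same formula gives 14–19 (2.9 months, placebo) and 6–8 (8.3 months, enzalutamide).

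**3. Apparent shift in a continuous marker when no patient changes.** Let Z be the standardised log2 marker, constant in each patient, with hazard λ0 × HR^Z. Choose λ0 so that the overall median stays at 4 months: E[exp(−4 λ0 HR^Z)] = 0.5. The mean among those still event-free at time t is E[Z S(t|Z)] / E[S(t|Z)], against 0 at baseline. The documents give no hazard ratio for any marker, so HR is an assumed range.

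| Assumed HR per SD | Loss by Week 9 | Loss by Week 13 |
|---|---|---|
| 1.0 | 0 | 0 |
| 1.3 | −0.08 SD | −0.12 SD |
| 1.5 | −0.13 SD | −0.19 SD |
| 2.0 | −0.22 SD | −0.31 SD |

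**4. The same for a binary marker.** Assume 35% prevalence, the middle of the 30–40% that Protocol 1.2 reports for AR-V7, used here only as a plausible value for a binary marker. At an assumed HR of 2, the equation 0.35 e^(−8λ0) + 0.65 e^(−4λ0) = 0.5 gives λ0 = 0.1340.

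- Week 9: 0.2137 / (0.2137 + 0.5079) = 29.6%.
- Week 13: 0.1670 / (0.1670 + 0.4490) = 27.1%.

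Prevalence goes from 35% to 27–30%. The corresponding range is 30–32% at HR 1.5 and 22–26% at HR 3.

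**5. The paired summary in the same scenario.** Each subject's later value equals his baseline value, so the paired change is exactly 0 at any HR.

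**The case against.** Several stronger readings are tempting, and the documents do not support them.

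- *All biomarker dynamics are cross-sectional.* They are not: AR-V7, the resistance marker best supported in the protocol, has a planned within-patient status change. That item does merge stable positive with stable negative, and it does not say which later sample counts.
- *Everyone who progresses by Week 13 has left.* Bone progression at Week 9 needs a confirmatory scan six or more weeks later, so it is confirmed after Week 13. No scan is scheduled between Weeks 9 and 17 (Protocol 5.3.1). Treatment may continue past progression with sponsor approval. The 11–15 is therefore an upper range for radiographic progression. Clinical progression could add some loss, which is not quantified here.
- *The SAP excludes the progression samples.* It lists them in section 2 and in 6.1.3. The word *scheduled* leaves their use undefined; it is not a rule against them.
- *The protocol expects these markers to predict early progression.* It says only that possible correlations will be explored, for sensitivity as well as resistance markers. Its AR-V7 citation concerns PSA response.

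The consequences are also bounded. The time courses are descriptive with no test of change, and N per marker will show the attrition. Random loss alone would give a standard error between the Week 13 and baseline means of √(1/25 − 1/40) = 0.12 SD to √(1/29 − 1/40) = 0.10 SD, so the shift at HR 1.3 is about the size of noise. The table layouts are in TLF specifications that are not in the public documents.

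All of this limits the size of the problem. None of it supplies a paired summary for the other markers or a stated use for the progression samples.

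**Conclusion.** The point holds in a limited form. Apart from AR-V7 status change, SAP 7.4.3 offers no within-patient measure for an objective that asks for dynamics, although the samples are serial and the same SAP computes within-subject change for laboratory tests and vital signs. The handling of the PSA-progression and radiographic-progression samples is undefined.

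The spurious fall depends on the marker being prognostic: none at HR 1, small at 1.3, and up to about 0.3 SD at 2.0 per SD. It also rests on exponential rPFS with a 4-month median and on loss near the upper range. The Cox and Fisher analyses of baseline markers do not use Week 13 samples and stand as planned. For an exploratory, descriptive endpoint this is a cheap improvement worth making; it does not threaten the trial's main conclusions.

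**What to change.** In SAP 7.4.3, keep the cross-sectional summaries and add the following.

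- For AR-FL, GR-FL and the inflammatory and neuroendocrine markers: within-subject log2 change from baseline at Week 13, PSA progression and radiographic progression, in subjects with both samples, with that subset's own baseline shown.
- For AR-V7, AR-V12, the composite, the AR mutations and CTC detection: paired baseline-to-later 2×2 tables.
- For AR-V7 level, AR-V12 level and the AR-V7/AR-FL ratio: change only in subjects positive at both times. The levels and the ratio are summarised for positive status only, so a subject who converts has no paired value and is counted in the 2×2 table.
- Baseline values for subjects with and without a Week 13 sample.
- The sampling occasions of SAP 6.1.3 in place of the reference to scheduled time points.

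The cost is SAP wording and table shells, with no new samples. The paired N is smaller, about 25–29 at Week 13 in the illustration. The paired result describes only subjects with both samples: it removes the artefact of comparing different groups, but it does not say what happened in those not sampled again.

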In the Phase III PREVAIL trial [Beer et al, 2014], 1717 men without prior chemotherapy exposure were randomized to receive enzalutamide or placebo. Compared to placebo, enzalutamide improved rPFS (rPFS rate at 12-month: 65% vs 12%; HR= 0.19; 95% CI, 0.15 to 0.23; P<0.001) and overall survival (HR=0.71; 95% CI, 0.60 to 0.84; P<0.001). The

benefit of enzalutamide was shown with respect to all secondary endpoints, including the time until the initiation of cytotoxic chemotherapy (HR= 0.35), the time until the first skeletal-related event (HR= 0.72), a complete or partial soft-tissue response (59% vs. 5%), the time until PSA progression (HR, 0.17), and a rate of decline of at least 50% in PSA (78% vs. 3%) (P<0.001 for all comparisons). Fatigue and hypertension were the most common clinically relevant adverse events associated with enzalutamide treatment.

No clinical data are available on activity of enzalutamide after sequential treatment with enzalutamide and chemotherapy. Modest activity of enzalutamide after therapy with abiraterone acetate and docetaxel were reported. The reported rate of ≥50% PSA decline range between13% to 46% [Bianchini et al, 2014; Azad et al, 2014; Schrader et al, 2014].

Clinical prevalence of biomarkers implicated in resistance has been reported. Approximately 30-40% patients have circulating tumor cells positive for ARv7 after enzalutamide or AA therapy [Antonarakis et al, 2014]. No PSA response was observed on either enzalutamide or abiraterone among these patients. ARv567es was reported to be expressed in at least 1 metastatic lesion among 71% of 13 subjects who underwent biopsy [Sun et al, 2010].

Rationale for Enzalutamide re-treatment

Benefit of re-treatment with a molecularly targeted agent after intervening therapies that are not cross-resistant with the initial therapies have been observed in other tumor types such as epidermal growth factor receptor (EGFR) tyrosine kinase inhibitor and in EGFR- mutant non-small cell lung cancer [Riely et al, 2007; Song et al, 2013].

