To date, a study of enzalutamide re-treatment following enzalutamide and intervening chemotherapy has not been performed. Limited data are available on re-treatment with an AR-targeting agent. A retrospective review of a small cohort of patients that received AA re-treatment (n=12), no biochemical response was observed among patients who did not initially respond to AA; among the 7 patients who initially responded to AA, upon re-treatment, the rate of PSA reduction by 30% and 50% was 86% and 46%, respectively. Given the similarity in MOA, evaluation of enzalutamide re-treatment in men with limited other therapeutic options is warranted [Leibowitz-Amit et al, 2014].

Rationale for chemotherapy prior to Enzalutamide re-treatment

Docetaxel may overcome resistance to enzalutamide in a manner that is both AR-dependent and AR-independent. Recent work suggests that the microtubule network of prostate cells is critical for androgen receptor nuclear translocation and activity. Unlike AR-V7, ARv567es/AR-V12 has hinge domain. This allows ARv567es/AR-V12 to co-sediment with microtubules or co-precipitate with dynein motor protein in the same way as AR-FL. Docetaxel was shown to suppress ARv567es/AR-V12 nuclear translocation and transcription activation [Thadani-Mulero et al, 2014]. In addition, being a cytotoxic agent, docetaxel has been shown to induce mitotic catastrophe subsequent to G2/M arrest, and activation of bcl-2 and bcl-xL gene dependent and independent apoptotic pathways [Fabbri et al, 2008]. This provides the AR-independent mechanism of overcoming the resistance. The study will enroll patients who have received at least 4 cycles of docetaxel and/or cabazitaxel to allow a

selection of a subset of patients for whom chemotherapy can overcome resistance. AR-V7 and AR-V12, as well as AR mutations will be studied to help assess response to enzalutamide re-treatment.

Cabazitaxel may overcome resistance to enzalutamide in a similar manner as docetaxel. Cases of reversions from AR-V7 positive to negative status following cabazitaxel treatment have been reported [Nakazawa et al, 2015].

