7 STATISTICAL METHODOLOGY

7.1 General Considerations

For continuous variables, descriptive statistics will include the number of subjects (n), mean, standard deviation, median, minimum and maximum. When needed, the use of other percentiles (e.g., 10%, 25%, 75% and 90%) will be mentioned in the relevant section.

Frequencies and percentages will be displayed for categorical data. Percentages by categories will be based on the number of subjects with no missing data, i.e., will add up to 100%.

All data processing, summarization, and analyses will be performed using SAS® Version 9.1.3 or higher on Unix. Specifications for table, figures, and data listing formats can be found in the TLF specifications for this study.

For the definition of subgroups of interest please refer to Section 7.8

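### SAP 7.4.3 item 2 prints AR-V7 switches as shares of all evaluable subjects, so it gives neither the reversion rate among baseline positives nor the conversion rate among baseline negatives

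*SAP*

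**What the plan says.** SAP 7.4.3 lists 19 biomarker items for descriptive summary. Item 2 is a single variable with three levels: "AR-V7 status change from baseline during the study (unchanged, positive to negative, negative to positive". Categorical items are reported as "N, frequency, and percentage for categorical variables", at baseline and at each scheduled time point afterwards.

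The denominator is set in two other places. SAP 5.4 says that the total N for each biomarker "will be the number of subjects with data available for that unique biomarker". SAP 7.1 adds: "Percentages by categories will be based on the number of subjects with no missing data, i.e., will add up to 100"%.

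Where the SAP wants a summary restricted to AR-V7 positives, it says so. Item 6, the AR-V7 to AR-FL ratio, is marked "for positive status AR-V7", and the continuous summaries in items 1 and 3 are limited to positives. Item 2 carries no such limit. Item 1 separately reports positive or negative status.

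The protocol synopsis gives as its first correlative objective: "Explore the prevalence and dynamics of resistance biomarkers". Item 2 is the only entry in the 7.4.3 list defined as a within-subject change.

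**The concern.** A subject can go from positive to negative only if positive at baseline, and from negative to positive only if negative at baseline. Three categories that add to 100% of everyone with data cannot use those two groups as denominators. Each switch is therefore divided by a total that includes subjects who could not make it. The result moves with baseline prevalence even when subjects behave the same way.

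The unchanged level also mixes two groups that the protocol treats as opposites. Protocol 1.2 reports no PSA response on enzalutamide or abiraterone among AR-V7-positive patients, so a subject who stays positive and one who stays negative are worth telling apart.

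At stake is how well the study describes biomarker dynamics. Anyone who takes the printed percentage for a reversion rate will read it as too small.

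**Working it through.** The documents give no figure for AR-V7 change, so there is none to reproduce. The check is algebra followed by examples.

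**Inputs.** At most 40 subjects (SAP 3.2). Baseline prevalence of 30-40%, from Protocol 1.2: "Approximately 30-40% patients have circulating tumor cells positive for ARv7 after enzalutamide or AA therapy". Carrying this range over to a population that has since had a taxane is an assumption. The numbers of pairs and of switches below are also assumed.

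**Formulas.** Let p be the share of paired subjects who are positive at baseline, r the reversion rate among them, and q the conversion rate among baseline negatives.

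- Printed positive to negative = p × r
- Printed negative to positive = (1 − p) × q
- Printed unchanged = p(1 − r) + (1 − p)(1 − q)

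The ratio of printed to conditional rate is p for reversion and 1 − p for conversion, whatever r and q are. At p = 0.30 the ratios are 0.30 and 0.70. At p = 0.40 they are 0.40 and 0.60. Reversion is thus understated by a factor of 1/0.40 = 2.5 to 1/0.30 = 3.3.

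**Examples with 40 pairs, the design maximum** (exact 90% intervals in brackets; the SAP plans none for this item):

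| | 12 positive, 28 negative | 16 positive, 24 negative |
|---|---|---|
| Half of the positives revert | 6 | 8 |
| Printed positive to negative | 6/40 = 15.0% (6.7-27.5) | 8/40 = 20.0% (10.4-33.2) |
| Among baseline positives | 6/12 = 50.0% (24.5-75.5) | 8/16 = 50.0% (27.9-72.1) |
| Printed figure if all revert | 12/40 = 30% | 16/40 = 40% |
| Unchanged, if no conversions | 34/40 = 6 positive + 28 negative | 32/40 = 8 positive + 24 negative |
| A quarter of the negatives convert: printed | 7/40 = 17.5% | 6/40 = 15.0% |
| Same, among baseline negatives | 7/28 = 25% | 6/24 = 25% |

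**Same printed figure, different behaviour.** With 30 pairs, 4 reversions among 4 positives and 4 among 20 positives both print as 4/30 = 13.3%. The conditional rates are 4/4 = 100% and 4/20 = 20%.

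**Can the cells be recovered from item 1?** Call the cells a (stays positive), b (positive to negative), c (negative to positive) and d (stays negative). Item 2 prints b, c and a + d. If item 1 at the same time point covers the same subjects, its positive count is a + c. Then a = (item 1 positives) − c, d = (a + d) − a, and paired baseline positives = a + b. In the 30-pair example with no conversions, item 1 would show 0 positives in one case and 20 − 4 = 16 in the other, so the two can be told apart.

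This works under two conditions:

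1. Item 2 must be tabulated at the same time point as item 1. The lead-in to 7.4.3 suggests this, but the item's own label refers to change during the study as a whole and does not say which sample decides. Samples are also taken at PSA and radiographic progression, which are not fixed visits.
2. Every subject with a later sample must have a baseline result. If u positive subjects lack one, item 1 shows a + c + u, and the derived number of paired baseline positives is too large by u.

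**The case against.** The strongest reply is that nothing here is wrong as description. The share of all evaluable subjects who switched is a valid quantity, the SAP calls the item status change and never calls it a reversion rate, and table layouts are left to a separate TLF specification that may already show four cells. Much of this stands. The printed percentage is correct for what it is, and the layout cannot be judged from the documents. But the SAP text calls for three categories and no conditional rate, so a four-cell display would go beyond what it specifies.

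Three stronger readings are tempting and are not supported.

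- *The table cannot be unpicked.* A reader might infer this from item 1's baseline count, which need not be paired. Item 1's post-baseline count does recover the cells under the two conditions above. What can be said is that the SAP does not guarantee them.
- *Item 2 tests the protocol's rationale.* Protocol 1.2 says: "Cases of reversions from AR-V7 positive to negative status following cabazitaxel treatment have been reported". Here the taxane comes before enrolment and baseline follows it, so that reversion would already have happened. Item 2 describes change during enzalutamide re-treatment. Its support is the general objective on dynamics.
- *The reversion figure is 60-70% too low.* This treats the 30-40% range as this trial's baseline prevalence. The range is not stated for patients who have since had a taxane, and the documents give no such figure. It also treats the conditional rate as the only legitimate target.

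**Conclusion.** The point holds as a minor one. Read with SAP 5.4 and 7.1, item 2 yields prevalence-weighted shares and one pooled unchanged group. That the printed figures equal p × r and (1 − p) × q is exact. The factors 0.30-0.40 and 0.60-0.70 hold only if baseline prevalence is 30-40%; a lower prevalence would dilute reversion more and conversion less.

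The effect is confined to a descriptive summary serving an exploratory objective. The rPFS analysis and sample size do not use item 2, and the Cox models and Fisher tests in SAP 7.4.3 use baseline predictors rather than status change.

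**What to change.** Replace item 2 by a baseline-by-post-baseline table of AR-V7 status in subjects with paired results, shown separately for Week 13, the PSA-progression sample and the radiographic-progression sample. It has four cells: stays positive, positive to negative, negative to positive, stays negative. Report positive to negative over paired baseline positives and negative to positive over paired baseline negatives, each with an exact 90% Clopper-Pearson interval. State that these row percentages are an exception to the SAP 7.1 rule, and show how many subjects have an unpaired sample.

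Both tools are already in the SAP: 7.5.2 plans shift tables for laboratory grades, and 7.4.2 uses exact 90% intervals. The cost is a short change to the SAP wording and one table shell, with no new data. The downside is smaller denominators and wider intervals: in the 12-positive example, 24.5-75.5% in place of 6.7-27.5%. That width reflects how few subjects can inform the question.
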